4.0 Test Schedule

4.1 Treatment with regorafenib

NOTE: Subjects should follow this test table while taking regorafenib regardless of treatment arm.

Tests and procedures	≤7 days prior to randomization	Active Monitoring Phase										End of All Treatment (within 30 days after last dose)	
		Cycle 1				Cycle 2				Prior to dosing each cycle beginning cycle 3+ (+/- 7 days)	Prior to dosing at restaging (C3 and every other cycle after) until progression (+/- 7 days)	End of Initial Treatment Mandatory Sequential Registration (if regorafenib is initial treatment) ¹²	
		Week 1 (Day 1)	Week 2 (Day 8)	Week 3 (Day 15)	Week 4 (Day 22)	Week 1 (Day 1)	Week 2 (Day 8)	Week 3 (Day 15)	Week 4 (Day 22)				
History and exam, weight, ECOG PS, blood pressure	X	X ⁷	X	X	X	X	X	X	X	X		X	X
Height	X												
Adverse event assessment	X				X				X	X		X	X
Hematology ⁵ CBC/ differential, ANC, INR/PTT ¹³	X	X ⁹				X				X			
Chemistry ⁵ SGOT (AST), alk phos, T. bili, serum creatinine, calcium, glucose, Na, K, SGPT (ALT), Mg	X	X ⁹		X		X		X		X			
Albumin ⁵	X	X ⁹			X				X				
Tumor Blood Bio-Markers (CEA)	X				X					X			
Tumor measurement ¹ (CT scan of chest, abdomen and pelvis), CT	X									X			X ⁶

component of a PET/CT, (MRI if CT is not feasible)												
ECG ⁴	X											
Serum pregnancy test ²	X	X ⁹										
Mandatory blood sample-plasma ^{10,R}		X				X						
STC1 biomarker blood collection ^R		X		X								
Mandatory tissue sample-archival tumor paraffin(see Section 17.0) ^{8, R}		X										
Patient Medication Diary (Appendix I) ³		X	X	X	X	X	X	X	X		X	X
Optional Blood sample -cfDNA Guardant 360 ^{10, 11, R}												X

1. CT scans preferred (MRI if CT is not feasible), CT component of a PET/CT, of the chest, abdomen and pelvis. Use same imaging throughout the study. Tumor measurements at baseline (≤ 28 days prior to randomization) and every 8 weeks beginning on cycle 3 day 1 prior to treatment until progression.
2. For women of childbearing potential only.
3. The diary must begin the day the patient starts taking the medication and must be completed per protocol and returned to the treating institution during each scheduled visit.
4. Performed at screening and then as needed.
5. Hematology and chemistry tests to be done prior to each cycle.
6. If patient goes off study during Cycle 1 and last CT scan was done > 28 days prior, the CT scan must be done.

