7.0 Protocol Treatment

Drugs will be administered in accordance with the information on the respective package inserts. Treatment will be given according to the schedule specified in the protocol. The terms “delay,” “modification,” and “omission” are defined as follows:

Delay: A delay indicates dose was postponed or not received when expected.

Modification: Indicates a change in dose level during the current cycle. However, if a modification was issued after the last dose was received in the current cycle, the modification should be reported on the subsequent cycle.

Omission: Indicates a dose was skipped and not made up, or that the drug was discontinued.

Arm A, treatment with regorafenib followed by anti-EGFR therapy (\pm irinotecan).

Arm B, treatment with anti-EGFR therapy (\pm irinotecan) followed by regorafenib.

Treatment on regorafenib will be continued in accordance with Section 7.11 “Planned treatment with regorafenib” until any of the “Criteria for discontinuing treatment with regorafenib” (Section 8.34) is met.

Treatment on Anti-EGFR therapy (\pm irinotecan) will be continued in accordance with Section 8.4, “Combination therapy of Anti-EGFR therapy (cetuximab (Cmab) **OR** panitumumab (Pmab) and irinotecan” until any of the “Criteria for discontinuing treatment including Cmab or Pmab” (Section 8.44) is met.

Patients assigned to Anti-EGFR therapy will receive either cetuximab or panitumumab per treating physician discretion and will be dosed per prescribing guidelines. Patients cannot switch between cetuximab and panitumumab during the course of the study. The use of irinotecan is per treating physician discretion and will be dosed per prescribing guidelines. If treating physician chooses to add irinotecan, irinotecan must be included in treatment starting at cycle 1.

7.1 Treatment Schedule - Use actual weight or estimated dry weight if fluid retention

Agent	Dose	Route	Frequency	ReRx
Regorafenib	80mg daily (Starting dose) See table 7.11	PO	Daily for Days 1-21 of 28 day cycle	Every 28 days
Cetuximab*	500mg/m ²	IV	Days 1, 15	Every 28 days
Panitumumab*	6mg/kg	IV	Days 1, 15	Every 28 Days
Irinotecan	180mg/m ²	IV	Days 1, 15	Every 28 days

* Patients assigned to Anti-EGFR therapy will receive **EITHER** cetuximab **OR** panitumumab, not both

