8.23 Hypertension

Hypertension is a known AE associated with regorafenib treatment. Subject will have their blood pressure measured at least weekly during the first 5 weeks of treatment. If additional blood pressure measurements are done outside the study site, and the blood pressure is >140 mm Hg systolic or >90 mm Hg diastolic (NCI CTCAE v5.0), then the subject must contact

study personnel. The management of hypertension, including the choice of antihypertensive medication, will be performed according to local standards and to the usual practice of the treating physician. Every effort should be made to control blood pressure by medical means other than study drug dose modification. If necessary, Tables Section 8.1 and 8.2 outline suggested dose reductions.

Table 8.23: Management of Treatment-Emergent Hypertension

Grade (CTCAE v5.0)	Antihypertensive Therapy	Regorafenib Dosing
1 Prehypertension (systolic BP 120 - 139 mmHg or diastolic BP 80 - 89 mmHg)	None	Continue regorafenib Consider increasing blood pressure (BP) monitoring
2 Systolic BP 140 - 159 mmHg or diastolic BP 90 - 99 mmHg, OR Symptomatic increase by >20 mmHg (diastolic) if previously within normal limits	Treat with the aim to achieve diastolic BP \leq 90 mm Hg: If BP previously within normal limits, start anti-hypertensive monotherapy If patient already on anti-hypertensive medication, titrate up the dose.	Continue regorafenib If symptomatic, hold regorafenib until symptoms resolve AND diastolic BP \leq 90 mm Hg ^a . When regorafenib is restarted, continue at the same dose level.
3 Systolic BP \geq 160 mmHg or diastolic BP \geq 100 mmHg OR More than one drug or more intensive therapy than previously used indicated	Treat with the aim to achieve diastolic BP \leq 90 mm Hg: Start anti-hypertensive medication AND/OR Increase current anti-hypertensive medication AND/OR Add additional anti-hypertensive medications.	Hold regorafenib until diastolic BP \leq 90 mm Hg, and if symptomatic, until symptoms resolve ^a When regorafenib is restarted, continue at the same dose level. If BP is not controlled with the addition of new or more intensive therapy, reduce by 1 dose level. If Grade 3 hypertension recurs despite dose reduction and antihypertensive therapy, reduce another dose level.
4 Life-threatening consequences (e.g., malignant hypertension, transient or permanent neurologic deficit, hypertensive crisis)	Per institutional guidelines	Discontinue therapy

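### Table 8.23 lets regorafenib restart on diastolic pressure alone, so an asymptomatic patient can be released while still grade 3 by systolic pressure

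*Combined protocol and SAP*

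**What the plan says.** The grade 3 row of Table 8.23 (section 8.23) has three alternative triggers: systolic 160 mm Hg or above, diastolic 100 mm Hg or above, or "More than one drug or more intensive therapy than previously used indicated". The treatment aim in the row is a diastolic pressure of 90 or below. The dosing cell reads "Hold regorafenib until diastolic BP" is 90 or below and, if the patient is symptomatic, until symptoms resolve. Regorafenib then restarts at the same dose level.

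Two dose rules follow in the same cell: "If BP is not controlled with the addition of new or more intensive therapy, reduce by 1 dose level", and "If Grade 3 hypertension recurs despite dose reduction and antihypertensive therapy, reduce another dose level". Footnote a takes patients who need more than 4 weeks' delay off protocol therapy.

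The text above the table leaves management to local standards and the physician's usual practice, and adds: "Every effort should be made to control blood pressure by medical means other than study drug dose modification". It also has patients contact study personnel if, on a measurement away from the site, "the blood pressure is >140 mm Hg systolic or >90 mm Hg diastolic".

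Section 8.0 requires sites to follow the modification tables strictly for the first two cycles and to treat them as guidelines afterwards.

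**The concern.** The hold can be triggered by systolic pressure alone, but systolic pressure plays no part in ending it. For an asymptomatic patient with systolic 160 or above and diastolic 90 or below, the release condition is already met when the hold starts. A site that follows the wording literally, as section 8.0 asks in cycles 1 and 2, could restart a patient who is still grade 3.

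This differs from the protocol's other regorafenib restart rules, which require recovery below the grade that triggered the hold:

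- Table 8.21: grade 3 toxicity must fall to grade 2 or lower.
- Table 8.22b: grade 3 hand-foot reaction must fall to grade 0-1.
- Table 8.24: transaminases above 5 times the upper limit of normal must fall below 3 times, or to baseline.

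The stake is patient safety during regorafenib treatment. Section 15.17 lists hypertensive crisis and posterior encephalopathy syndrome among rare but serious events, and section 15.198 links the latter to hypertension.

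**Working it through.** **Release check.** All patients below are asymptomatic, and the pressures are illustrative. A patient is grade 3 by pressure if systolic is at least 160 or diastolic is at least 100. The written rule releases if diastolic is at most 90. Two alternatives add a systolic condition of below 160, or of at most 140.

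| Pressure | Grade 3 by pressure now? | Written rule | Systolic <160 added | Systolic <=140 added |
|---|---|---|---|---|
| 178/84 at onset | Yes (178 >= 160) | Releases (84 <= 90) | Holds | Holds |
| 165/88, treated from 175/104 | Yes (165 >= 160) | Releases (88 <= 90) | Holds | Holds |
| 170/95 | Yes (170 >= 160) | Holds (95 > 90) | Holds | Holds |
| 155/88 after treatment | No | Releases | Releases | Holds |

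The written rule fails in the first two rows and works in the third. It also works when symptoms are present, because symptom resolution is then required.

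**Search for a systolic release value elsewhere.**

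- Criterion 3.26 has a systolic limit of 140, but it governs entry.
- The 140/90 contact rule in section 8.23 governs when a patient must contact study personnel.
- Section 8.1 reduces the dose for significant drug-related toxicity, a term it does not define.
- Table 8.21 excludes hypertension.
- The footnotes to Table 8.23 cover delay, re-escalation and the number of reductions.
- Section 8.3 mandates stopping for grade 4 hypertension and otherwise leaves it to the physician's safety judgement.

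None sets a systolic condition for restart.

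**Size.** The documents do not give the share of patients who are asymptomatic with systolic 160 or above and diastolic 90 or below, so the number affected cannot be computed. The expected number of all grade 3 or higher cases can be, assuming that the 7.2% in section 1.5 applies:

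- 30 patients (right-sided Arm A only): 0.072 x 30 = 2.16, with a binomial 95% range of 0 to 5. The chance of no case is 0.928^30 = 0.106.
- 72 patients (full expected accrual in section 16.22, including 12 left-sided patients, all assumed to take regorafenib): 0.072 x 72 = 5.18, range 1 to 10. The chance of no case is 0.928^72 = 0.005.

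These are expected counts of a wider group and are not upper limits.

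**The case against.** The best reply is that the literal reading would rarely be acted on. Section 8.23 leaves hypertension management to local standards and the treating physician, and section 8.3 lets the physician stop regorafenib for safety. Few physicians would restart at 178/84.

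The row itself also steps up antihypertensives and reduces the dose if pressure stays uncontrolled. If criterion 3.26 (systolic above 140 or diastolic above 90) is read as the protocol's benchmark for control, a patient who stays at 165/88 on stepped-up therapy would restart one level lower. Footnote a caps the delay at 4 weeks. The visit schedule in section 4.1 lists "History and exam, weight, ECOG PS, blood pressure" weekly in cycles 1 and 2, the only period in which the tables bind strictly, so a released patient would be seen again within about a week. Section 7.0 adds: "Drugs will be administered in accordance with the information on the respective package inserts". The inserts may guide a systolic restart, but they were not available to check.

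All of this lowers the practical risk, and it is why the point is minor. None of the provisions in the protocol supplies the missing condition. Dose reduction changes what the patient restarts on and does not extend the hold. Weekly measurement detects the problem but gives no value to act on. Criterion 3.26 is an eligibility rule that the table does not cite.

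The objection to the counts also stands: they describe all grade 3 or higher hypertension, and the figure for 72 assumes that every patient reaches regorafenib, although moving to sequential treatment is at the physician's discretion (sections 13.5 and 13.6).

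**Conclusion.** The concern holds, as a minor safety wording gap. In the grade 3 row, the written release condition can be met by an asymptomatic patient who is still grade 3 by systolic pressure, and nothing else in the documents closes this. That conclusion rests on the wording alone and is firm.

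Its practical frequency is not established. The number of patients affected may be zero. The 7.2% rate comes from a trial of standard dosing at 160 mg daily, whereas this trial starts at 80 mg and escalates weekly, so its transfer is uncertain. No effect on the overall survival comparison is shown.

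**What to change.** In the grade 3 row of Table 8.23 only, add a systolic condition to both the treatment aim and the release: systolic below 160 mm Hg together with diastolic at or below 90. The patient is then no longer grade 3 by pressure at restart. This fits the rest of the table, which lets asymptomatic grade 2 patients (systolic 140-159) continue regorafenib.

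The sponsor's clinicians could choose a stricter value, such as 140 or below, to parallel the diastolic limit and the contact rule. That would hold more patients (155/88 in the table above, for example) and sits less easily with the instruction to control pressure by means other than changing the study drug dose. Neither value addresses the third trigger, which is not a pressure reading.

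The cost is one row of wording in the next amendment, with no new scheduled measurements. Some patients would be held longer, and a few could reach the 4-week exit in sections 8.13 and 8.3.

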8.24 Liver Function Abnormalities

For patients with observed worsening of serum liver tests considered related to regorafenib (i.e. where no alternative cause is evident, such as post-hepatic cholestasis or disease progression), the dose modification and monitoring advice in Table below should be followed.

Regorafenib is a UGT1A1 inhibitor. Mild, indirect (unconjugated) hyperbilirubinemia may occur in patients with Gilbert's syndrome.

Table 8.24: Dose delay/modifications for ALT and/or AST and/or bilirubin increases related to study drug

Increases in AST/ALT (per NCI-CTCAE v 5.0)	1st Occurrence	Restart	Re-occurrence
AST and/or ALT \leq 5 X ULN (< Grade 3)	Continue dosing, with weekly monitoring of liver function until transaminases return to <3 X ULN (\leq Grade 1) or baseline.		
ALT and/or AST $>$ 5 X ULN (\geq Grade 3)	Interrupt dosing, with weekly monitoring until transaminases return to <3 X ULN or baseline.	If the potential benefit for reinitiating regorafenib/ placebo is considered to outweigh the risk of hepatotoxicity: Reduce one dose level and measure serum liver tests weekly for at least 4 weeks.	Discontinue
ALT and/or AST $>$ 20 X ULN (\geq Grade 4)	Discontinue		
ALT and/or AST $>$ 3 X ULN (\geq Grade 2) with concurrent bilirubin $>$ 2 X ULN	Discontinue treatment and measure serum liver tests weekly until resolution. Exception: patients with Gilbert's syndrome who develop elevated transaminases should be managed as per the recommendations outlined above for ALT/AST elevations.		

During the first 2 cycles of treatment, ALT, AST and bilirubin must be monitored every 2 weeks.

8.3 Criteria for discontinuing treatment with regorafenib

Treatment with regorafenib will be discontinued if any of the following criteria for discontinuation is met:

1. When regorafenib is considered to be ineffective
 - Radiographically confirmed disease progression.
 - Significant worsening of symptoms or physical findings (disease progression should be radiographically confirmed whenever possible).

2. When treatment with regorafenib cannot be continued
 - It is necessary to reduce the dose of regorafenib to less than dose level -2 according to the criteria for dose reduction/modification of treatment.
 - Treatment cannot be resumed within 28 days after modification of treatment due to an adverse event.
 - A 3rd episode of grade 3 hand-and-foot syndrome occurs despite symptomatic treatment and dose reduction of regorafenib.
 - Grade 4 hypertension.
 - Grade 4 or higher increase in AST/ALT, 2nd episode of grade 3 increase in AST/ALT or bilirubin > upper limit of normal x 2 and AST or ALT > upper limit of normal x 3.
 - Other grade 4 non-hematological toxicity.
 - The treating physician decides that treatment with regorafenib cannot be continued due to safety concerns.
3. Patient's request for discontinuation of treatment with regorafenib.
4. After enrollment, the patient is found to be ineligible for the study, and it is concluded that further treatment with regorafenib is detrimental to him/her.
5. Transfer to another institution for any reason during treatment with regorafenib.

8.4 Combination therapy of Anti-EGFR therapy (cetuximab (Cmab) OR panitumumab (Pmab)) and irinotecan

Treatment with cetuximab/panitumumab or irinotecan will be started if it is confirmed that all criteria for treatment are met prior to treatment initiation. If all criteria for starting treatment with Cmab/Pmab are met, but any of the criteria for starting treatment with irinotecan is not met, only Cmab/Pmab can be administered. If the case is reversed, however, irinotecan should not be administered alone (without Cmab/Pmab).

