3.1 Inclusion Criteria

- 3.11 Age \geq 18 years.
- 3.12 Histologically proven, unresectable distant metastatic or locally advanced Colorectal adenocarcinoma with primary tumor site from right-sided disease only (cecum, ascending colon, hepatic flexure, and transverse colon).
- 3.13 KRAS, NRAS wild type.
- 3.14 BRAF v600E wildtype.
- 3.15 Measurable disease as defined in Section 11.0.
- 3.16 ECOG Performance Status (PS) 0, 1, or 2. (Form is available on the ACCRU web site:
[REDACTED]
- 3.17 Life expectancy of \geq 3 months per estimation of treating physician.
- 3.18 The following laboratory values obtained \leq 7 days prior to randomization.

- Absolute neutrophil count (ANC) $\geq 1200/\text{mm}^3$
 - Platelet count $\geq 75,000/\text{mm}^3$
 - Hemoglobin $\geq 9.0 \text{ g/dL}$
 - Total bilirubin $\leq 1.5 \times$ upper limit of normal (ULN)
 - Alanine aminotransferase (ALT) and aspartate amino-transferase (AST) $\leq 2.5 \times$ ULN ($\leq 5 \times$ ULN for subjects with liver involvement of their cancer)
 - Serum creatinine $\leq 1.5 \times$ ULN
 - INR/PTT $\leq 1.5 \times$ ULN
- NOTE: Patients who are therapeutically treated with an agent such as warfarin or heparin will be allowed to participate provided that no prior evidence of underlying abnormality in coagulation parameters exists. Close monitoring of at least weekly evaluations will be performed until INR/PTT is stable based on a measurement that is pre-dose as defined by the local standard of care.
- Alkaline phosphatase limit $\leq 2.5 \times$ ULN ($\leq 5 \times$ ULN for patients with liver involvement of their cancer)

- 3.19a Negative serum pregnancy test done ≤ 7 days prior to randomization for women of childbearing potential only. NOTE: Post-menopausal women (defined as no menses for at least 1 year) and surgically sterilized women are not required to undergo a pregnancy test. The definition of adequate contraception will be based on the judgment of the treating physician.
- 3.19b Provide informed written consent.
- 3.19c Willing to return to enrolling institution for follow-up (during the Active Monitoring Phase of the study).
- 3.19d Disease progression on or intolerable to any of the following: fluoropyrimidine, oxaliplatin and irinotecan.
- 3.19e Able to swallow and retain oral medication.
- 3.19f Willing to provide tissue and blood samples for correlative research purposes (see Sections 6.0, 14.0 and 17.0).

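### Section 8.3 stops regorafenib on a combined bilirubin and transaminase criterion without exception, while Table 8.24 exempts patients with Gilbert's syndrome from the same criterion

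*Combined protocol and SAP*

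**What the plan says.** Section 8.3 opens with an unconditional instruction: "Treatment with regorafenib will be discontinued if any of the following criteria for discontinuation is met". Among the criteria it lists is "bilirubin > upper limit of normal x 2 and AST or ALT > upper limit of normal x 3". That item mentions no cause, makes no exception and does not point to Section 8.24.

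Section 8.24 has a narrower scope. It is written "For patients with observed worsening of serum liver tests considered related to regorafenib", which it explains as cases "where no alternative cause is evident, such as post-hepatic cholestasis or disease progression". The title of Table 8.24 repeats the limit: "Dose delay/modifications for ALT and/or AST and/or bilirubin increases related to study drug". For ALT and/or AST above 3 x ULN with bilirubin above 2 x ULN the action is "Discontinue treatment and measure serum liver tests weekly until resolution". An exception follows in the same row: patients with Gilbert's "syndrome who develop elevated transaminases should be managed as per the recommendations outlined above for ALT/AST elevations".

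Three other places bear on the point.
- Section 3.18 requires total bilirubin of at most 1.5 x ULN at entry. It allows AST/ALT up to 2.5 x ULN, or up to 5 x "ULN for subjects with liver involvement of their cancer".
- Section 8.0 makes the modification tables strict for the first two cycles and guidelines after that.
- Section 7.0 continues regorafenib until one of its discontinuation criteria is met. It cites these as Section 8.34, a number that does not exist; the section with that title is 8.3.

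**The concern.** Both sections set a rule at the same numerical threshold, but only one carries the Gilbert's exception and only one is limited by attribution. Section 15.17 lists hepatotoxicity as regorafenib's boxed warning, so sites should not be able to read its hepatic stopping rule in two ways.

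The stop also matters to trial conduct. Under Section 8.6, meeting a regorafenib stopping criterion moves an Arm A patient towards sequential treatment, which must begin within 28 days if protocol treatment is to go on. In Arm B it ends protocol treatment. A stop without progression then feeds the rules in Section 16.32: censoring of PFS1 before sequential treatment starts, re-registration as the starting point of PFS2, and censoring of stPFS when sequential treatment is not begun or is left early.

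**Working it through.** The plan gives no figure to reproduce and no arithmetic applies. The check sets the two sections side by side, case by case. Every case below has bilirubin above 2 x ULN and is not a radiographic progression.

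| Case | Section 8.3 | Section 8.24 / Table 8.24 | Result |
|---|---|---|---|
| Related, no Gilbert's, ALT/AST >3 x ULN | Stop | Stop | Agree |
| Related, Gilbert's, ALT/AST >3 to 5 x ULN | Stop | Continue with weekly monitoring | Conflict |
| Related, Gilbert's, ALT/AST >5 to 20 x ULN, first occurrence | Stop | Interrupt; restart one dose level lower is possible | Conflict |
| Related, Gilbert's, recurrence >5 x ULN, or any value >20 x ULN | Stop | Stop | Agree |
| Not related (e.g. post-hepatic cholestasis), ALT/AST >3 x ULN | Stop, if read literally | Outside the table's scope; no instruction | Unclear |

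Example: a patient with Gilbert's syndrome has ALT 4 x ULN and bilirubin 2.5 x ULN. Since 4 > 3 and 2.5 > 2, the Section 8.3 criterion is met and regorafenib stops. Under Table 8.24 the exception applies and 4 ≤ 5, so dosing continues with weekly monitoring.

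**Can such a patient be in the trial?** Yes. Gilbert's syndrome is not among the exclusions in Section 3.2. A patient with bilirubin at or below 1.5 x ULN can enter, and Section 8.24 itself expects bilirubin to rise in these patients because regorafenib inhibits UGT1A1.

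**Does another section settle it?** No. Section 8.0 makes Table 8.24 binding for the first two cycles, so in that period a site cannot obey both. Later the table becomes a guideline while 8.3 keeps its mandatory wording, but nothing says that the exception is meant to lapse then. Section 7.0 points to a section number that does not exist and sets no order of precedence.

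**Does the text imply an attribution condition in 8.3?** Not clearly. Section 8.0 is headed as modification for adverse events, but Section 10.0 defines an adverse event regardless of drug relation, so the heading supplies none. Against that, the item after the liver item in 8.3 refers to other grade 4 non-hematological toxicity, which suggests that the items before it are toxicities too.

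**Who falls in the unclear row?** Mainly patients with a non-drug cause and no progression, because radiographic progression stops regorafenib under item 1 of 8.3 in any case. A patient with liver involvement who entered with AST/ALT above 3 and up to 5 x ULN, as 3.18 allows, and stays there, needs only a rise in bilirubin above 2 x ULN to meet the literal wording.

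**The case against.** The strongest reply is that 8.3 is a short summary list and Table 8.24 the detailed rule, so a sensible reader would carry the table's qualifiers across. That is a plausible intention, but no section states it, and the wording of 8.3 is mandatory. For Gilbert's patients the reply fails.

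It has more force on attribution. A reader might infer that the sections give opposite orders for unrelated worsening as well. The documents do not support that: 8.24 is silent there and does not instruct the site to continue, and 8.3 can be read as a list of toxicities. This half is a mismatch of scope that needs clarifying.

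A reader might also infer that a patient entering with AST/ALT above 3 x ULN is close to a mandatory stop from the day of randomisation. The criterion needs both parts, and 3.18 caps bilirubin at 1.5 x ULN at entry, so no eligible patient meets it then. That cap has no Gilbert's allowance, so it also keeps out Gilbert's patients with higher baseline bilirubin and shrinks the group in true conflict.

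Finally, it would be wrong to size the problem by counting all patients with liver involvement, or by treating each affected patient as a full patient's share of an arm's exposure. The documents give no rate for liver involvement, Gilbert's syndrome or the combined abnormality, and one early stop removes only part of one patient's treatment time.

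**Conclusion.** The contradiction is established for one group: patients with Gilbert's syndrome, bilirubin above 2 x ULN and a first occurrence of ALT/AST above 3 and up to 20 x ULN. For them 8.3 and Table 8.24 cannot both be followed. The missing attribution condition in 8.3 is a secondary ambiguity, mainly for non-drug causes without progression.

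The size cannot be calculated from the documents. Several conditions must coincide in a trial of about 60 right-sided patients, so the number affected is probably small; that is a judgement, not a derived figure.

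A reader might infer a bias in the primary comparison. The documents do not show one. Overall survival runs to death whether or not treatment has stopped, and neither its definition, the 26 evaluable patients per arm nor the 42-death trigger depends on this rule. What can change is when regorafenib stops, when or whether sequential treatment starts, and how PFS1, PFS2 and stPFS are censored. Both arms receive regorafenib, so both can be affected, at different points in the sequence. In Arm A the effect also reaches the second treatment phase.

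**What to change.** Reconcile Sections 8.3 and 8.24. State the combined bilirubin and transaminase criterion once, and have the other section refer to it. The single statement should say:

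- whether the Gilbert's exception applies;
- whether the criterion depends on attribution to regorafenib, and so what happens with a non-drug cause such as post-hepatic cholestasis;
- how it applies to patients with liver involvement who entered above 3 x ULN under 3.18.

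Correct the reference to Section 8.34 in Section 7.0 in the same change. Which clinical rule is right is for the sponsor to decide.

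The cost is one protocol wording change and a notice to sites. It needs no new tests and no change to the sample size or the analysis.
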